6.1.5 Suspected unexpected serious adverse reactions

A suspected unexpected serious adverse reaction (SUSAR) is an unexpected adverse drug reaction, which also meets the definition of SAE.

6.2 Methods of recording and assessing adverse events

Few AEs have been reported following ivermectin, albendazole, or ivermectin-albendazole co-administration in STH infected individuals. The most common AEs were abdominal cramps, headache, fatigue, nausea, diarrhoea, fever, and vertigo. Such symptoms can, however, also result from the infection itself. Such side effects may be more frequent and/or serious in patients with a heavy worm burden.

The observation time for AEs starts when the treatment is initiated. Participants will be observed for at least three hours following treatment for any acute AE and reassessment will be done at 24 hours and 14-21 days post-treatment. If there is any abnormal finding, the local study physician will perform a full clinical examination and findings will be recorded. An emergency kit will be available on site to treat any medical conditions that warrant urgent medical intervention. Participants will also be interviewed

iverped_protocol_v1.2_20240508

at three and 24 hours as well as at 14-21 days after treatment about the occurrence of AEs. Any potential

AEs happening between three hours post-treatment and the further follow-up time points (24 hours and

14-21 days) will be monitored and managed with the help of the locally based medical team (including

specifically trained community health workers, nurses and medical doctors). Medical intervention will

be provided if necessary.

Information on all AEs (incidence, intensity, seriousness and causality) will be entered immediately in

the appropriate AE module of the CRF. For all AEs, sufficient information will be pursued and/or

obtained so as to permit i) an adequate determination of the outcome of the event (i.e. whether the event

should be classified as a SAE); and; ii) an assessment of the casual relationship between the AE and the

study treatments. Intensity of AE will be judged by the study physician, following guidelines by the

European Medicines Agency (Note for Guidance on Clinical Safety Data Management).

All SAEs, unexpected adverse drug reactions or SUSARs must be reported as described in Section 6.3.

6.3 Reporting of serious adverse events

Any study-related unanticipated problem posing risk of harm to participants or others (including all

unexpected adverse drug reactions), and any type of SAE will be immediately (within a maximum of

24 hours after becoming aware of the event) notified to the study sponsor-investigator and Co-PIs:

[name]. [name] (Sponsor-Investigator/PI)

Swiss Tropical and Public Health Institute

[name]

[contact]

[contact]

E-mail: [contact]

[name] [name] (Co-PI)

Public Health Laboratory Ivo de Carneri

[name]

[contact]

E-mail: [contact]

Within the following 48 hours, the local co-investigator must provide further information on the SAE

or the unanticipated problem in the form of a written narrative to the study sponsor-investigator. This

should include a copy of a completed SAE form, and any other diagnostic information that will assist

the understanding of the event. In exceptional circumstances, a SAE may be reported by telephone. In

these cases, a written report must be sent immediately thereafter by fax or e-mail. Names, addresses and

telephone for SAE reporting will be included in the trial-specific SAE form. Relevant pages from the

CRF may be provided in parallel (e.g., medical history, concomitant medications).

6.4 Safety reporting to Health Authorities, Ethics Committees and other third parties

The sponsor-investigator will send appropriate safety notifications to Health Authorities in accordance with applicable laws and regulations. Additionally, this information will be provided to the responsible ethics committees in Switzerland and Zanzibar according to national rules. Fatal or life-threatening SAEs or SUSARs will be reported within 24 hours followed by a complete report within 7 additional calendar days. Other SAEs and SUSARs that are not fatal or life-threatening will be filed as soon as possible but no later than 14 days after first knowledge by the sponsor-investigator. SAEs involving ivermectin ODTs will be reported to the manufacturer.

6.5 Rescue medication strategy

In case an adverse event requires medical intervention, this will be performed by the study physician and in accordance with local medical guidelines. Given the most common adverse events (headache, abdominal pain, itching, nausea, vomiting and diarrhoea), analgesics and antipyretics (*e.g.* paracetamol) are allowed to be given to participants in case of pain or fever, antiemetics (*e.g.* dimenhydrinate) to prevent nausea and vomiting and/or antibiotics to prevent or treat bacterial superinfection. In addition, electrolyte replacement solution in case of severe vomiting and diarrhoea, immunosuppressants (*e.g.* dexamethasone) in case of allergies or immune system over-reaction (*e.g.* due to a high amount of worms being expulsed) or an adsorptive antidote (*e.g.* activated charcoal) may be administered.

At the end of the study, all participants remaining positive for *T. trichiura* or any co-infection will be treated with the currently best recommended treatment.

7. Data management and data quality control

The investigators are responsible for an adequate data quality. Prior to the initiation of the study, a short investigator's meeting will be held between investigators of Swiss TPH and PHL-IdC. This meeting will include a detailed discussion of the protocol, performance of study procedures (standard operating procedures from previous studies available on site), CRF completion, specimen collection and diagnostic methods.

7.1 Source data

Source data are comprised of clinical findings and observations as well as laboratory data maintained and compiled at the study site. Source data are contained in hardcopy source documents and are allowed to be accessed by local authorities. Source data will be directly entered in the following documents:

- CRF: Primary data collection instrument for the study. It holds records of all clinical and
 physical examination data, treatment information and AEs. For every participant enrolled in the
 clinical trial a corresponding CRF exists. All data requested on the CRF must be recorded, and
 investigators will review and approve each CRF for completion.
- 2. Census: Holds name, age and sex of each potential participant.

- 3. Laboratory parasitology sheets: Record of the *T. trichiura*, *A. lumbricoides* and hookworm egg counts at all sample collection time points.
- 4. PK: Time records of PK sample collection.

7.2 Data collection and documentation

Data collected and produced within this trial will fall into one of the following categories:

- a) Egg counts of *T. trichiura*, *A. lumbricoides* and hookworm derived from quadruplicate Kato-Katz microscopy performed at baseline as well as at 14-21 days post-treatment.
- b) Anthropometric and clinical characteristics of the trial participants collected using the study's CRF such as weight, height, blood pressure, temperature, overall health status and any abnormal medical condition or chronic disease.
- c) Finger prick blood samples for haemoglobin measurement and PK analysis.
- d) Collection date and time of each PK sample.
- e) Measured concentrations analysed from finger prick blood samples and subsequently derived PK parameters.

All data categories will be recorded paper-based (primary data source), *e.g.* on the CRF, and double-entered into the electronic data collection software REDCap (Vanderbilt University, US) using tablets. In this case, the paper-based data will represent the primary data source. All entries will be printed in blue ink and all corrections must be documented with date and initials of the respective team member. Double-entered data will be compared using the REDCap internal 'Data Comparison Tool' and any discrepancies will be reviewed against the hardcopies of the CRF and corrected accordingly. All data files in REDCap will be merged into a master file and saved as .xlsx and/or .csv file. Data analysis will be conducted with pseudonymised data and reporting of findings will be fully anonymised.

7.3 Ethical, legal and security issues

Information about study participants will be kept confidential and managed accordingly. Screened participants will be listed in a confidential "participant screening log" and attributed a unique participant ID (PID). In case of enrolment, participants will be listed in a confidential "participant enrolment log" utilizing the same PID. The PID will be linked with the participant's identity on a separate file (participant identification list), filed in a secured place at PHL-IdC. This document will constitute the only source to decode the pseudonymised data and will only be accessible to investigators. Personal data will be coded for data analysis. No names will be published at any time, and published reports will not allow for identification of single participants. Confidentiality will be ensured throughout the entire research project. All databases will be password secured. None of the investigators declare to have any conflicts of interest.

7.4 Data storage and preservation

All samples containing biological material will be destroyed after completion of the study. Paper-based and electronic source data and related material will be preserved for a minimum of 15 years to enable understanding of the study procedures, which allows the work to be assessed retrospectively and repeated if necessary. The study site (PHL-IdC) will retain the original hardcopy source documents such as CRFs to ensure that local collaborators can provide access to these documents to a monitor, auditor, or regulatory agency. Essential infrastructure such as a locked room for safe storage of hardcopy data will be made available. Electronic copies of source documents will be transferred to Swiss TPH, Allschwil, Switzerland, for storage on secured network drives with restricted access for study personnel only. The primary storage of electronic data will be within REDCap on the Swiss TPH shared server and strictly confidential by password protection. The entire REDCap project (including all data) will be backed up regularly, *e.g.* weekly. Secondary data storage will be on personal, password-protected laptops of the PI and Co-PIs, and on a flash drive kept by Co-PIs at the study site.

7.5 Study documents: translations – reference language

- The protocol master document will be in English, all further language versions (*e.g.* Kiswahili) are translated thereof.
- The ICF master document will be in English, all further language versions (*e.g.* Kiswahili) are translated thereof.
- The CRF master document will be in English, all further language versions (*e.g.* Kiswahili) are translated thereof.

8. Statistics

8.1 Definition of primary endpoint

T. trichiura infection status 14-21 days post-treatment assessed by quadruplicate Kato-Katz is the primary endpoint in our study.

8.2 Justification of number of trial participants

The main aim of this study is to elucidate the nature of the dose-response relationship. A series of simulations was carried out to determine the required sample size. We assumed different sets of true CRs ranging from very optimistic (10%, 45%, 54%, 58% and 60%) to very pessimistic (15%, 30%, 33%, 34% and 35%) for 0, 100, 200, 300 and 400 μ g/kg, respectively. Assuming a loss to follow-up of 10%, we estimated that enrolling 35 participants per arm will be sufficient to predict the dose-response curve with a precision (defined as median distance between prediction and confidence band) of about 10 %-points in the relevant dose range from 100 μ g/kg to 400 μ g/kg. Additionally, 35 individuals will be included for the standard tablet arm. In total, we anticipate to recruit 210 participants.

The suggested sample size of a maximum 5 PK samples from 24 participants (12 per concerned study arm) is sufficiently high to determine the population PK parameters with a sparse sampling scheme.

8.3 Description of statistical methods

The primary analysis will use the full analysis set (available case population) according to the intention-to-treat principles defined as all randomised participants who provide any follow-up data. Only randomised participants not providing follow-up data as well as participants who were negative at baseline and erroneously randomised will be excluded from the analysis. In addition, a per-protocol analysis will be conducted. Eligibility for analysis sets will be determined before unblinding. CRs will be calculated as the percentage of egg-positive participants at baseline who become egg-negative after treatment.

EPG will be assessed by adding up the egg counts from the quadruplicate Kato-Katz thick smears and multiplying this number by a factor of six. Geometric and arithmetic mean egg counts will be calculated for the different treatment arms before and after treatment to assess the corresponding ERRs (see formula).

$$ERR = 1 - \frac{\frac{1}{n} e^{\sum \log(EPG_{follow-up} + 1)} - 1}{\frac{1}{n} e^{\sum \log(EPG_{baseline} + 1)} - 1}$$

Bootstrap resampling method with 5,000 replicates will be used to calculate 95% confidence intervals (CIs) for ERR point estimates. Using the DoseFinding package of the statistical software environment R, hyperbolic E_{max} models will be implemented to predict the curves of the dose-response in terms of CRs and ERRs.

Previous similar trials have shown that the proportion of participants lost to follow-up is usually far below 10%, therefore, no imputation of missing data will be performed. Infection status and egg counts of participants with incomplete data at follow-up (*i.e.* only one stool sample available at follow-up) will be estimated based on the available data. This means a participant is considered infected if any sample is positive and EPGs will be calculated as mean egg count of the available sample multiplied by 12.

The safety analysis set will include all treated participants. AEs will be evaluated descriptively focusing on the proportion of participants reporting symptoms before and after treatment in each arm.

Previously established nonlinear mixed-effects (NLME) models will be used to compare and determine PK parameters [21]. Concentrations are measured with a validated LC-MS/MS method [32]. Using NLME, the following key PK parameters will be calculated:

- C_{max} maximal plasma concentration
- t_{max} time to reach C_{max}

- AUC area under the curve, from 0 to 24 h and 0 to inf.
- $t_{1/2}$ elimination half-life

 C_{max} and t_{max} will be observed values derived from the plasma concentration-time profile. Total drug exposure (AUC) and $t_{1/2}$ will be calculated with the WinNonlin software package using compartmental analysis. The elimination half-life will be estimated by the equation: $t_{1/2} = \ln 2/\lambda$, where λ (the elimination rate constant) will be determined by performing a regression of the natural logarithm of the concentration values during the elimination period. Primary PK parameters including absorption rate (k_a), volume of distribution (V), and clearance (CL) will be estimated utilizing NLME modelling. In addition, exploratory pharmacometric PK and exposure-response analyses may be performed with the Monolix or NONMEM software package.

The VAS score for the palatability will be summarised using descriptive statistics according to formulation (ivermectin ODT, and ivermectin standard tablets crushed and swallowed with water). Each of the arms receiving the new formulation (arm A, B, C, D and E) will be tested against the current formulation (Arm F).

9. Duties of the investigator

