For the initial diagnosis and efficacy assessment at 14-21 days posttreatment, two stool samples will be collected from each participant on two consecutive days. All stool samples will be examined for presence of T. trichiura, A. lumbricoides, and hookworm eggs with duplicate Kato-Katz thick smears assessed via bright-field microscopy. The medical history of the participants will be assessed with a standardised questionnaire, in addition to a clinical examination carried out by the study physician before treatment. Parents/caregivers will be interviewed before treatment and at three and 24 hours and 14-21 days post-treatment for the occurrence of AEs. Any potential AEs happening between 3 hours and the respective follow-up time points will be monitored by local healthcare workers and medical intervention provided if necessary. Each participant will be asked to provide a finger-prick blood sample for haemoglobin measurement at baseline. At the same time, anthropometric measurements (i.e. height, and weight) will be taken for all participants.

To determine PK parameters of ivermectin ODTs and standard tablets, a subsample of 12 study participants per relevant treatment arm (ivermectin ODT 200 μ g/kg and ivermectin tablet 200 μ g/kg) will be asked to provide a maximum of 5 micro blood samples per participant using finger pricks at defined time points between 1 hour and 24 hours. To determine the acceptability of ivermectin ODTs compared to standard tablets, the palatability of each formulation will be rated by children aged 4-5 years using a 100 mm visual analogue scale (VAS). Additionally, participants will complete a short questionnaire right after treatment administration.

Statistical analyses

An available case analysis (full analysis set according to the intention to treat principles) will be performed, including all participants with primary endpoint data. Additionally, a per-protocol analysis will be conducted. CRs will be calculated as the percentage of egg-positive participants at baseline who become egg-negative after treatment.

Geometric and arithmetic mean egg counts will be calculated for the different treatment arms before and after treatment to assess the corresponding ERRs. Bootstrap resampling with 5,000 replicates will be used to calculate 95% confidence intervals (CIs) for ERRs.

	Using the DoseFinding package of the statistical software environment
	R , E_{max} models will be implemented to predict the dose-response curves

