The **secondary objectives** of the trial are:

- a) to determine the *T. trichiura* egg reduction rates (ERRs) of treatments;
- b) to determine the CRs and ERRs of treatments against *Ascaris lumbricoides* and hookworm co-infection;
- c) to evaluate the safety and tolerability of the treatments.
- d) to characterize population PK of ivermectin ODTs compared to standard tablets in *T. trichiura* infected individuals;
- e) to assess the acceptability of the treatments.

The **exploratory objective** of this trial is to assess the diagnostic performance of FECPAKG2.

4. Methodology

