9.1 Investigator's confirmation

This trial will be conducted in accordance with the protocol, International Conference on Harmonisation Good Clinical Practice E6 (R2) (ICH-GCP) and the current version of the Helsinki Declaration.[36, 37] All protocol modifications must be documented in writing. A protocol amendment can be initiated by either the Sponsor-Investigator/PI or any Co-PI. The Investigator will provide the reasons for the proposed amendment in writing and will discuss with the Sponsor-Investigator/PI and Co-PIs. Any protocol amendment must be approved and signed by the Sponsor-Investigator/PI and must be submitted to the appropriate Independent Ethics Committee (IEC) for information and approval, in accordance with local requirements, and to regulatory agencies if required. Approval by IEC must be received before any changes can be implemented, except for changes necessary to eliminate an immediate hazard to trial participants, or when the change involves only logistical or administrative aspects of the trial, *e.g.* change of telephone number(s).

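### The egg reduction rate formula in section 8.3 has 1/n outside the exponential, so as written it does not give the geometric-mean ERR that the text describes

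*Combined protocol and SAP*

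**What the plan says.** Section 8.3 states "Geometric and arithmetic mean egg counts will be calculated for the different treatment arms before and after treatment to assess the corresponding ERRs (see formula"), and the formula follows directly. It is one minus a ratio. The numerator is "1}{n} e^{\sum \log(EPG_{follow-up} + 1)} - 1" and the denominator is "1}{n} e^{\sum \log(EPG_{baseline} + 1)} - 1" (both in LaTeX source, picked up after the opening of the fraction 1/n). In each, 1/n stands in front of e as a multiplier and the exponent holds only the sum of logs.

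The Synopsis (Statistical analyses) describes the same plan in words and gives no formula: "Geometric and arithmetic mean egg counts will be calculated for the different treatment arms before and after treatment to assess the corresponding ERRs". No other section gives a second ERR formula or corrects this one.

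The ERR is used in several places. *T. trichiura* ERR is secondary objective (a) in section 3, and objective (b) is "to determine the CRs and ERRs of treatments against" *A. lumbricoides* and hookworm. Section 8.3 adds 95% bootstrap intervals from 5,000 replicates and says that hyperbolic Emax "models will be implemented to predict the curves of the dose-response in terms of CRs and ERRs".

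**The concern.** The log(EPG + 1), exponentiate, subtract 1 pattern is that of a geometric mean. A geometric mean needs the nth root of the product, so 1/n has to be in the exponent. Outside it, the formula divides a very large product by n. The ratio of two such products is roughly the true ratio of means raised to the power n, so the result depends on the number of children as well as on the treatment effect.

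The trial exists to describe a dose-response relationship. An ERR that sits near 100% in every arm with a moderate or large reduction cannot contribute to that, and its bootstrap interval would collapse towards 100% too. ERRs for *T. trichiura* and the co-infections would not be comparable, because the numbers infected differ.

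**Working it through.** The documents state no numerical ERR, so there is no figure to reproduce. The check evaluates the formula as written against the version with 1/n in the exponent.

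**Inputs**
- Formula and bootstrap: section 8.3.
- n per arm: 35 enrolled, 10% loss assumed (section 8.2), so 35 × 0.9 = 31.5, taken as 32.
- Baseline geometric mean: not given. Assumed 300 EPG, with a range of 100 to 1000.
- Co-infected children per arm: not given. Assumed 10.

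**Algebra**
- exp(Σ log(EPG + 1)) = Π(EPG + 1) = (GM + 1)^n, where GM is the geometric mean as usually defined with the +1 shift.
- Term as written: (GM + 1)^n / n − 1. Term intended: [Π(EPG + 1)]^(1/n) − 1 = GM.
- Because (GM + 1)^n is enormous at these arm sizes, the divisor n cancels and the −1 is negligible. As written, ERR ≈ 1 − [(GM_fu + 1)/(GM_bl + 1)]^n, with fu for follow-up and bl for baseline.

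**Sanity checks on the mean term**
- 35 children all at 0 EPG: 1/35 − 1 = −0.971, impossible for an egg count. The correct value is 0.
- 35 children all at 300 EPG: 301^35/35 − 1 ≈ 1.6 × 10^85. The correct value is 300.

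**Hand checks on the ERR**
- Three children each falling from 300 to 150 EPG. As written: 1 − (151³/3 − 1)/(301³/3 − 1) = 1 − 1,147,649.3/9,090,299.3 = 87.4%. With 1/n in the exponent: 1 − 150/300 = 50.0%.
- Three children at 120, 480, 600 EPG falling to 0, 24, 120. The products of (EPG + 1) are 121 × 481 × 601 = 34,978,801 and 1 × 25 × 121 = 3,025. As written: 1 − 1,007.3/11,659,599.3 = 99.99%. Geometric: 1 − 13.46/326.04 = 95.87%. Arithmetic: 1 − 144/1200 = 88.0%.

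**At the planned arm size (n = 32, baseline GM 300 EPG)**

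| True change in GM | Ratio raised to the power 32 | ERR as written |
|---|---|---|
| 1% reduction | (298/301)^32 = 0.726 | 27.4% |
| 5% reduction | (286/301)^32 = 0.195 | 80.5% |
| 10% reduction | (271/301)^32 = 0.0347 | 96.5% |
| 25% reduction | (226/301)^32 = 0.000104 | 99.99% |
| 50% reduction | (151/301)^32 = 2.6 × 10^−10 | 100.0% |
| 10% increase | (331/301)^32 = 20.9 | about −1991% |

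**Where it saturates.** The formula gives 99% when the ratio is 0.01^(1/32) = 0.866. Then GM_fu = 301 × 0.866 − 1 ≈ 259.7, a true reduction of about 13.5%. Any bootstrap replicate of 32 children with a larger reduction therefore gives at least 99%.

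**Sensitivity to the assumed baseline.** For 100 to 1000 EPG, a 5% reduction gives 80.3–80.6%, a 10% reduction gives 96.4–96.6%, and the 99% threshold is 13.4–13.5%.

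**Dependence on n.** With n = 10 a 10% reduction gives 1 − (271/301)^10 = 65.0%, against 96.5% with n = 32. The 99% threshold moves to about 37%.

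**The case against.** The strongest objection is that the whole point rests on where 1/n sits relative to a superscript in one displayed equation that was machine-read from a PDF. Numerator and denominator agree, which makes a single stray misreading less likely, but the same layout could be misread twice. This stands as a reason to look at the original page first.

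Second, the intention is clear. The words geometric mean and the log(EPG + 1) structure leave no serious alternative, and a mean of 10^85 EPG would be noticed at once, so the code may well be right. That is likely, and it is why this is called a notation slip. But the equation is the plan's only ERR formula: correct code would depart from it, and code that follows it would be wrong.

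Third, arithmetic-mean ERRs are also planned and are untouched, and section 8.3 does not say which ERR enters the bootstrap and the Emax fit. The effect on those two steps therefore applies to the geometric ERR, the only one for which a formula is given.

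Finally, ERR is secondary and can be recalculated from retained egg counts. That limits the consequence but does not make the formula correct.

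**Conclusion.** The concern holds for the equation as it appears in the extracted text. The expression is not a geometric mean for any n above 1 in general, and at 32 children per arm it reports at least 99% for any true reduction of about 13.5% or more. The algebra needs no assumption. The percentages assume a baseline geometric mean of 300 EPG and n = 32; they barely change between 100 and 1000 EPG but depend strongly on n.

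If the formula were followed literally, the geometric-mean ERRs under secondary objectives (a) and (b), their bootstrap intervals and an Emax curve fitted to them would be uninformative about dose until recalculated. The cure-rate endpoint, its Emax curve, the sample size and trial conduct are not affected. It should be corrected before analysis.

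**What to change.** Check the equation on the original page. If 1/n is in the exponent there, nothing needs changing. If it reads as above, replace it with

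`ERR = 1 − [exp((1/n) Σ log(EPG_follow-up + 1)) − 1] / [exp((1/n) Σ log(EPG_baseline + 1)) − 1]`

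Label it the geometric-mean ERR, and use it wherever section 8.3 relies on that formula, including the bootstrap and the ERR Emax fit. The planned arithmetic-mean ERRs stay as they are. Confirm that the analysis code matches; the three-child example falling from 300 to 150 EPG should return 50.0%.

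The cost is one line of text. Section 9.1 requires modifications in writing and says "Any protocol amendment must be approved and signed by the Sponsor-Investigator/PI and must be submitted to the appropriate Independent Ethics Committee (IEC"), so the correction should go through that route. Section 9.1 exempts purely logistical or administrative changes from prior ethics approval; whether a notation correction qualifies is for the sponsor to settle. Conduct, data collection and sample size do not change.
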